A recent publication by Morretti et al [4] evaluated the effect of different doses of oral iron in non-pregnant iron deficient young women. They evaluated the effect of varying doses of daily ferrous sulfate and once and twice daily dosing of ferrous sulfate on hepcidin levels and fractional and total iron absorption. Women were treated with a single daily dose ranging from 40-240mg of elemental iron. This 6-fold increase in elemental iron dosage only resulted in a 3 fold increase in the amount of elemental iron absorbed, contradicting the notion that more iron is better. In a second arm of the study, women were treated with twice daily dosing for a total of 180mg of elemental iron. **The results of the study demonstrated that 24 hours after a dose > 60mg, hepcidin increased and fractional iron absorption decreased by 35-45%. Multiple daily doses did not increase iron absorption beyond single daily dosing.** The authors concluded that providing daily dosages less than 80mg of elemental iron and avoiding

twice daily dosing maximized iron absorption. **The results of the study by Morretti et al challenge the conventional wisdom that more severe iron deficiency anemia in pregnancy is best treated by increasing from daily to twice daily supplementation. Morretti et al also did not evaluate for gastrointestinal side effects or increase in hemoglobin.**

Given the high incidence of iron deficiency anemia in pregnancy and the associated complications, we propose a prospective, randomized double blinded clinical trial to evaluate the optimal dosing of oral iron supplementation in pregnancy. We will recruit mothers identified as having iron deficiency anemia at the time of routine prenatal blood work in the second trimester. These subjects will be randomized to daily or twice daily ferrous sulfate 325mg (65mg of elemental iron). The primary outcomes will be hemoglobin concentration at the time of admission for delivery and post-partum and assessment of gastrointestinal side effects. The secondary outcome will be frequency of blood transfusion at the time of delivery.

Hypothesis: Once daily dosing of ferrous sulfate 325mg/dL will be associated with increased maternal hemoglobin concentration at the time of delivery and post-partum and decreased gastrointestinal side effects.

Specific Aims

1. Determine whether once daily dosing of oral iron is more effective in raising maternal Hgb concentration than twice daily dosing.

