This will be a prospective, randomized, double blinded placebo controlled clinical trial. Subjects will be identified for possible enrollment during the second trimester during routine prenatal care. Criteria for enrollment will be a singleton intrauterine gestation as above. Subjects without anemia will have weekly questionnaires regarding GI symptoms during otherwise scheduled prenatal visits. Subjects with iron deficiency anemia as diagnosed by an Hgb concentration of less than 10.5-11mg/dL per ACOG guidelines and a ferritin of less than 15mg/dL will be randomized to once or twice daily iron supplementation by means of a computer generated random number list by the investigational drug pharmacy. The study drug will be provided by the University of Missouri Investigational Drug Pharmacy under the guidance of [name], the Investigational Drug Pharmacist for the University. Iron supplementation will be in the form of ferrous sulfate 325mg (65mg of elemental iron) once or twice daily. Anemic subjects will receive identical packs of drug with instructions to take one pill BID (twice daily). The morning pill will be ferrous sulfate 325mg. The evening pill will be randomized to contain either ferrous sulfate 325mg or placebo. The placebo will be produced by the investigational drug pharmacy and contain cellulose, a biologically inert plant fiber. The subjects and investigators will be blinded to assignment. As part of standard Obstetric care, the subject will have a hemoglobin repeated at the time of admission to labor and delivery and on post-partum day 1. Subjects who are not anemic will serve as controls and not receive a prescription. This is appropriate as the standard of care is not to treat non-anemic women with iron supplementation.

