- The type and timing of the data to be collected for withdrawn subjects.
All data collected from a withdrawn subject will immediately be destroyed.
- Whether and how subjects are to be replaced.
To replace withdrawn subjects, we will recruit another pregnant mother
- The follow-up for subjects withdrawn from investigational product treatment/trial treatment.
There will be no follow-up.

Data handling:

All data will be coded with an ID number. The key containing the ID numbers will be kept in a locked file separate from the data. Data generated from samples tested for this study will be stored by the MU Biorepository and by the research staff. . The data will be kept for 7 years after study completion. This data will not be shared with outside investigators or used for research other than this study. Additionally, data from this study will be included in the Prospective Obstetric Database (PODS) study for future use in de-identified fashion.

Data Analysis

Statistical Analysis: Statistical analyses will be performed using the IBM SPSS statistical software version 22 (IBM Corporation, Armonk, NY, USA). ANOVA will be used to assess the difference in mean hemoglobin at the time of admission and post-partum in the three arms for the study. Regression analysis will be used to explore the relationships of iron supplementation on maternal hemoglobin at delivery and fetal hemoglobin, hepcidin, and ferritin while controlling for maternal ferritin and hepcidin at enrollment. A planned secondary analysis will be to use a Chi-square or Fisher's exact test as appropriate to examine the incidence of blood transfusion during the admission for delivery. Significance will be set at $P \leq 0.05$.

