Power Analysis: The mean hemoglobin concentration in pregnancy is about 12mg/dL and the standard deviation is about 1mg/dL. At an alpha of 0.05 a sample size of 17 subjects in each arm would be required to have 80% power to detect a difference of 1mg/dL in maternal hemoglobin. In order to account for subjects lost to follow up due to delivery at other facilities, transfer of care and a 20% lost to follow up rate, we will continuously enroll subjects until 50 subjects are randomized to treatment in order to preserve adequate power to assess our primary outcomes and control for covariates in the setting of lost to follow up. The prevalence of anemia in pregnancy is reported to be between 8 and 27% in the second and third trimesters of pregnancy[1]. As such, we anticipate a total sample size of around 250 (50 subjects on treatment divided equally between once and twice daily iron and 200 controls receiving routine prenatal care. Our facility delivers around 2000 patients per year, most of whom receive care in our clinics. As such, we anticipate being able to recruit our target sample size, including accounting for patient drop out and replacement, in 12-18 months. Based on prior published data [5], 10 subjects per arm are required to identify a difference gastrointestinal symptoms.

Anticipated results and future directions

Based on the increased hepcidin and reduced fractional absorption seen with multiple daily dosing, I anticipate that once daily dosing will be superior to twice daily dosing in

the treatment of anemia diagnosed during the second trimester of pregnancy. In this case, I plan a follow up study to evaluate once versus twice daily dosing in anemia diagnosed in the first trimester (1-14 weeks gestation), which is less common but may represent a more severe depletion of iron stores. **If twice daily dosing is proven to be equivalent or superior to once daily dosing in pregnancy, I plan a study similar to that of Morretti to determine if the changes in hepcidin levels seen with multiple daily doses of iron in the non-pregnant patient are also seen in pregnancy. It is possible that pregnant women have a less robust increase in hepcidin in response to oral iron and can benefit from increasing dosage. It is also possible that they would have a more robust response and would be better served with less frequent (i.e.) every other day dosing.** I plan to use preliminary data from this study to apply for external funds to answer these questions.

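### The named hemoglobin test is a three-arm ANOVA that includes non-randomized, non-anemic controls; no once-versus-twice-daily contrast is specified to answer Aim 1

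*Combined protocol and SAP*

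**What the plan says.** All references are to the combined protocol and SAP.

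- **Specific Aims, Aim 1:** "Determine whether once daily dosing of oral iron is more effective in raising maternal Hgb concentration than twice daily dosing". This is a comparison of the two iron regimens.
- **Study Design:** only women with iron deficiency anemia are randomized. The third group is defined by not having the condition: "Subjects who are not anemic will serve as controls and not receive a prescription".
- **Data Analysis, Statistical Analysis:** ANOVA is to assess the "difference in mean hemoglobin at the time of admission and post-partum in the three arms for the study", with significance at P ≤ 0.05. No pairwise contrast, post-hoc test or confidence interval is mentioned. The second hemoglobin analysis reads "Regression analysis will be used to explore the relationships of iron supplementation on maternal hemoglobin at delivery", with adjustment for enrollment ferritin and hepcidin.
- **Data Analysis, Power Analysis:** 17 per arm gives "80% power to detect a difference of 1mg/dL in maternal hemoglobin", taking an SD of about 1. The plan randomizes 50, split equally, allows for a "20% lost to follow up rate", and expects "200 controls receiving routine prenatal care".
- **Anticipated results and future directions:** one follow-up study is planned if once daily is superior. Another is planned under the condition "If twice daily dosing is proven to be equivalent or superior to once daily dosing in pregnancy". No section gives an equivalence margin, test or interval criterion.

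**The concern.** The question asked and the test named do not match. Aim 1 asks about two randomized groups of anemic women. The overall F test asks whether any of three means differ, and the largest group was selected for not being anemic. If treated women have not fully caught up with the controls by delivery, the F test can be significant even when the two regimens perform identically. A reader given that P value could not tell whether once daily differs from twice daily, by how much, or in which direction.

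The comparison that does answer Aim 1 is protected by randomization, but as the plan stands it would be chosen after the analysis begins. Without an interval for that difference, a null result also cannot be read. Nothing would show whether a difference of the size the trial was designed to detect has been excluded. The loose use of the word equivalent in the future-directions section adds to this, but it is a side issue.

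**Working it through.** **Inputs from the plan:** SD 1; target difference 1; alpha 0.05 (sidedness not stated); power 80%; 25 randomized per regimen; 200 controls; 20% loss. Hemoglobin is in the plan's own units throughout.

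**Assumed, because the documents do not give it:** how far the control mean lies above the treated mean at delivery, taken as 0.25, 0.5 or 0.75.

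**1. Reproduce the plan's sample size.** A two-sided, two-sample t test with difference/SD = 1/1, alpha 0.05 and power 80% solves to 16.7, which rounds up to 17 per arm. Power at 17 is 80.7%. A one-sided normal calculation gives 13, which does not match. So the 17 per arm is correct, and it is the size for a two-group comparison, not for a three-group ANOVA.

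**2. Completers.** 25 × 0.8 = 20 per regimen; 200 × 0.8 = 160 controls.

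**3. ANOVA when the two regimens are identical.** Put both treated means at μ and the control mean at μ + δ. The noncentrality parameter is

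λ = [(20 + 20) × 160 / 200] × δ² / SD² = 32 δ².

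The critical value is F(0.95; 2, 197) = 3.04. From the noncentral F distribution:

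| δ (assumed) | λ | Probability that ANOVA is significant |
|---|---|---|
| 0.25 | 2 | 22% |
| 0.5 | 8 | 71% |
| 0.75 | 18 | 97% |

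With no loss in any arm (25/25/200), λ = 40 δ² and the figures are 27%, 81% and 99%. The result does not depend on the loss assumption. It does depend on δ.

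**4. What the randomized contrast would deliver.** The 95% CI half-width for once minus twice is t(0.975, 38) × SD × √(2/20) = 2.024 × 0.316 = 0.64. With 17 per arm it is 0.70, and with 25 it is 0.57.

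**5. How often a null result would leave the target difference open.** For 20 per arm and truly equal regimens, by simulation with 2,000,000 draws, a non-significant result whose 95% CI reaches 1.0 in either direction occurs in about 21% of all trials. Counting the upper limit alone gives 11%. If the true difference is 0.5, the contrast is non-significant 66% of the time.

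**The case against.** *The regression supplies the contrast.* This is the strongest counter-argument. If iron supplementation were coded by regimen, the model would give an adjusted once-versus-twice coefficient, and the Power Analysis mentions preserving power to control for covariates. But the coding is not stated, the stated purpose is to explore relationships, and for maternal hemoglobin the regression names delivery but not post-partum. It could become the answer to Aim 1; the plan does not make it so.

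*The control differences are assumed.* True: no section supplies them, and treatment may close the gap, so the percentages illustrate and do not predict. The structural point does not need them, because an overall F test over three groups does not isolate one pair at any value of δ.

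*The equivalence wording is only a remark about future work.* This stands. It is not an aim, hypothesis or decision rule, and equivalent and superior lead to the same follow-up study.

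A reader might go further and infer that this is an equivalence trial with its margin missing, or that the sponsor will read P > 0.05 as equivalence. The documents support neither. The aims and hypothesis are framed as superiority of once daily, the sample size is for a difference, and no rule ties the word proven to a non-significant P value.

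**Conclusion.** The concern holds as a mismatch between Aim 1 and the named hemoglobin test. The textual basis is firm: the third arm is non-randomized, the ANOVA covers all three arms, and no once-versus-twice contrast or interval is specified. The practical size depends on the unknown control difference. Under equal regimens, SD 1 and 20/20/160 completers, the chance of a significant ANOVA that says nothing about Aim 1 runs from 22% to 97% over assumed differences of 0.25 to 0.75.

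It does not follow that the sample size is wrong. The 17 per arm reproduces, and 20 completers per regimen exceeds it. Nor does it follow that the trial cannot answer Aim 1, since the data for the randomized comparison will be collected. What is missing is the commitment to make that comparison the reported result. This is worth correcting, at modest weight. The equivalence wording is a minor editorial note.

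**What to change.** In Data Analysis, Statistical Analysis, add:

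> The primary hemoglobin comparison is the once-minus-twice-daily difference in means among randomized subjects, reported with its 95% CI at admission and post-partum. The three-arm ANOVA including non-anemic controls is descriptive and does not answer Aim 1. A non-significant P value will not be reported as equivalence; the CI will be used to state which differences are and are not excluded.

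In Anticipated results and future directions, replace the words equivalent or superior with a condition such as *if superiority of once daily is not shown*, or justify an equivalence margin before unblinding. Which follow-up study an inconclusive result leads to is for the sponsor to say.

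**Cost:** wording in two sections, ideally before unblinding, and one named comparison on data already planned. No extra subjects, visits or samples are needed. The three-arm ANOVA loses its primary role, and the sponsor gives up the word equivalent unless it justifies a margin. How to handle two time points that disagree, or multiplicity across them, is a separate question that this text does not settle.
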